# A Multi-Center Study on the Utility of Non-invasive Carboxyhemoglobin and Total Hemoglobin Measurement in Emergency Department Patients

## SUNE0002 version 3

---

- b. The threshold of SpHb will be determined by receiver operating curve analysis of the pooled results from the first set of 500 subjects for each institution.
- c. Validate the SpHb threshold that predicts the outcome of “acute treatment of anemia” using a second set of subjects of 500 subjects from each institution.

Secondary objectives:

1. Measure extent of agreement between SpHb and total Hb determined by central hospital laboratory. Total Hb determined by blood gas analyzer will also be compared to the central laboratory measurement.
2. Survey the provider to determine the impact of the screening test. Providers will be asked: Did SpHb screening expedite care of patients? Did SpHb screening identify occult anemia?

### 3 STUDY DESIGN

This is a prospective, nonrandomized, multi-center study of the performance of simultaneous non-invasive testing for two common disorders (COP and anemia). We will determine the limits of agreement and performance characteristics of non-invasive SpCO and SpHb values compared to standard blood tests for measurement of COHb and hemoglobin, in the emergency department setting.

### 5 SUBJECT SELECTION AND WITHDRAWAL

#### 5.1 Number of Subjects

At least 3000 subjects across three sites may be enrolled onto this study. We expect to enroll approximately 1000 subjects at each site. This sample size is based on previous experience that has have demonstrated: 1) Occult toxicity occurs in approximately 1-3/10,000 ED visits. 2) Higher numbers of CO, needed to determine extent of agreement between non-invasive and laboratory measurements, are infrequent.

#### 5.2 Inclusion Criteria

- Age 1 year or older.
- At least one digit has acceptable width as measured by study-provided digit gauge.
- Presenting to emergency department for any complaint.
- Potential for IV catheter and/or blood draw for CBC as standard of care.

---

# A Multi-Center Study on the Utility of Non-invasive Carboxyhemoglobin and Total Hemoglobin Measurement in Emergency Department Patients

## SUNE0002 version 3

---

### 5.3 Exclusion Criteria

- Patients who are unable to consent and also surrogate consent was unable to be obtained.
- Patients with fingernail polish, discoloration or trauma to fingers.

### 5.4 Study Timelines

Subject participation in this study is not expected to delay any care or prolong their stay in the ED. The study will be conducted approximately between October 1, 2016 and December 31, 2018. We anticipate enrolling an average of 10 patients a day.

**Subject Recruitment** Patients may be screened at triage with FDA approved oximeter devices as part of standard of care procedures. The results of this screening will be recorded in the chart if performed, by clinical staff as per routine procedure.

A convenience sample of patients aged 1 year and up presenting to the emergency department for any complaint and who have received or will receive a blood test for CBC or an IV catheter during their care (determined by their care provider independently) or will be approached by trained research staff for evaluation for enrollment in the study.

We will also approach patients with known CO exposure or who have anemia to enroll them in this study. The attending emergency physician will conduct usual clinical care; research staff will seek to obtain informed consent for this part of the study.

Research staff will also be notified of any patient presenting to the emergency department with suspected CO exposure (e.g. rescued from fire), toxicity or anemia, or patients with signs and symptoms of CO toxicity (unexplained headache, nausea, vomiting, dizziness or lightheadedness, syncope, neurological deficits, shortness of breath). The treating provider will be notified if the patient has agreed to participate. If the clinician determines an IV is necessary, these patients will also be eligible for inclusion in the study.

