#### 1.1 Background and Rationale

Carbon monoxide (CO) is the leading source of poisoning in the US and elsewhere. CO poisoning (COP) can cause severe disability and death. CO is released whenever there is combustion of fossil fuels including wood, oil, kerosene, etc. The diagnosis of COP is made when exposure to CO occurs and there are signs and symptoms consistent with toxicity. Exposure can be determined either with measurement of environmental CO levels or carboxyhemoglobin (COHb) concentrations in the blood. COP can cause headache, nausea, vomiting, dizziness, syncope, loss of consciousness, coma, focal neurological deficits, psychiatric manifestations and cardiac ischemia. Because CO is colorless, tasteless and has no odor, patients may not know if they have been exposed. Universal screening with a blood test is not feasible and not typically performed. Many of the signs and symptoms associated with COP are non-specific and may be attributed to other conditions if CO exposure is not considered. Patients could therefore be released from the hospital to return to an environment with CO potentiating toxicity, leading to death or severe disability. The use of environmental CO detectors has increased in public facilities and private homes in the US, but screening of emergency medicine subjects for CO exposure is not yet a standard practice. A device which estimates COHb concentrations non-invasively using a finger probe has been approved by the FDA and utilized in clinical care. This device passes 8 separate frequencies of light through the fingertip and measures absorbance at those frequencies during pulsatile blood flow, allowing estimation of pulse oximetry (Sp) hemoglobin species (Oxyhemoglobin: SpO2, total hemoglobin: SpHb, carboxyhemoglobin SpCO, and methemoglobin: SpMet). We have used this device at Rhode Island Hospital to screen patients who presented for any complaint and showed that 1-4/10,000 patients had unsuspected (both to the patient and clinician) COP. The sources of exposure were often faulty exhaust systems or dysfunctional appliances in the home. Other investigators have replicated these findings in Vermont (unpublished), Europe and Turkey. Studies which have evaluated the accuracy of the device when compared to blood COHb measurements have shown variable results. Taken together, these studies show that sensitivity of the device has utility for COP screening, but it does not have the accuracy to replace blood COHb.

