
The device manufacturer has developed a new diagnostic platform that allows for simultaneous measurement of SpO2, SpCO and SpHb, with modifications that may improve diagnostic performance. Most emergency department routinely measure SpO2 during triage, and some (such as Rhode Island Hospital) also measure SpCO. Enhancement of the triage oxyhemoglobin profile to include total Sp CO and SpHb could provide significant benefit in a busy emergency department setting.

Determination of anemia rapidly in the Emergency Department may prevent morbidity and mortality. Patients with traumatic injuries causing hemorrhage, occult internal hemorrhage (GI bleeding, ectopic pregnancy, etc.), hemolysis, or other critical anemias, could be quickly identified. Triage nurses could then expedite physician evaluation and acquisition of blood samples for type and cross. Screening for anemia is subjectively performed by observing for pallor in the skin and mucous membranes (in particular, the palpebral conjunctiva). However, studies have shown that this method is not reliable. Validation of a non-invasive screening method that may be utilized in the pre-hospital setting or in emergency department triage could prevent complications associated with delays in diagnosis of anemia by blood analysis.

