### 1.2 Study Device

SpHb and SpCO technology uses a multiwavelength sensor with various light emitting diodes (LEDs) that pass light through the measurement site to a detector as shown in the figure below. Signal data is obtained by passing various visible and infrared lights (LEDs, 500 to 1400nm) through a capillary bed (for example fingertip) and measuring changes in absorption during the blood pulsatile cycle. The detector receives the light and converts it to an electrical signal which is, in turn, used to predict SpHb and SpCO.

[figure not shown]

Figure 1 Masimo technology overview

Devices used for SpHb and SpCO measurement evaluation consist of a Masimo Rainbow pulse CO-oximeter (e.g. Masimo Rad-67, investigational) connected to a fingertip sensor (e.g., Masimo DCI Mini Super sensor, investigational). The investigational devices used in this study employ similar material and technology compared to FDA-cleared devices. The investigational devices have undergone risk analysis and safety testing in accordance with applicable safety standards, including electrical safety, current leakage, mechanical safety and biocompatibility testing for patient contacting materials. That risk assessment concluded that the investigational devices do not pose unmitigated risks to operator or subject.

The Rad-67 is a prototype handheld pulse CO-oximeter with Rainbow technology similar to already cleared Masimo noninvasive pulse CO-oximeters and is intended for spot-check measurements on patients in various care area settings (hospitals, hospital-type facilities, and clinics). The device is a more compact version of 510(k) cleared Rad-57 and Pronto devices. The Rad-67 also comes with an upgraded display with touchscreen capabilities. The Masimo Rad-67 is intended to be used with Masimo sensors and patient cables.

---

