### SpCO:

1. Measure extent of agreement between SpCO and COHb determined by co-oximeter measurement of blood in the emergency department.
2. Determine diagnostic performance characteristics of SpCO (sensitivity, specificity, False Positive and False Negative) compared to gold standard of laboratory measurement of COHB in whole blood using a co-oximeter. We will define *a priori* a “true positive” of COHb  $\geq 7$  for COP.
  - a. We will also dichotomize smokers and non-smokers, and perform a post-hoc analysis to determine if the use of an alternate threshold for “true positive” based on smoking history is feasible.
3. Determine utility of SpCO for screening purposes by surveying the provider to determine the impact of screening test. Providers will be asked: Did the patient have a CO poisoning clinical diagnosis? Did SpCO screening lead to identification of occult toxicity?
4. Determination of elimination pharmacokinetics of CO in emergency department patients with CO toxicity as related to method of O2 administration (nasal cannula, non-rebreather mask, CPAP, or endotracheal intubation). Clinicians will administer O2 as dictated by patient care, the method and amount of O2 will be recorded. CO elimination will be evaluated as a function of FiO2.

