# A Multi-Center Study on the Utility of Non-invasive Carboxyhemoglobin and Total Hemoglobin Measurement in Emergency Department Patients

## SUNE0002 version 3

---

recorded on the case report forms (CRF). Demographic information, height, weight, gender, age, skin color, vital signs (heart rate, blood pressure, respiratory rate, pulse oximetry), presence or absence of jaundice, smoking history will be recorded on CRFs along with the values of SpCO, SpHb, COHb and hemoglobin concentration. If an abnormal COHb (>10%) value is observed, the measurement will be repeated using a Masimo FDA-cleared pulse CO-oximeter (e.g. Rad-57 and DCI sensor). If abnormal values are confirmed, the patient's clinician will be notified by research staff immediately. The clinician will independently determine any course of action related to patient care utilizing this information. CRFs will be kept within a locked filing cabinet in the Emergency Medicine Research Office which is locked. A de-identified data spread sheet will be created and kept on a storage device with encryption.

Stage 2: We will also approach patients with known CO exposure or who have anemia to enroll them in an arm of this study. Research staff will be notified of any patient presenting to the emergency department with suspected CO exposure or toxicity including patients with signs and symptoms of CO toxicity (headache, nausea, vomiting, rescued from fire, unexplained neurological deficits) or who have low hemoglobin values for any reason determined as part of their routine care. The treating provider will be notified if the patient has agreed to participate and if the clinician determines an IV is necessary, these patients will also be eligible for inclusion in the study.

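### Patients flagged by a triage SpCO reading can be recruited as suspected CO cases, so pooled SpCO sensitivity may be overstated, and the plan neither records nor analyses entry route

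*Combined protocol and SAP*

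**What the plan says.** Section 5.4 (Subject Recruitment) allows routine triage oximetry before enrolment: "Patients may be screened at triage with FDA approved oximeter devices as part of standard of care procedures". It continues: "The results of this screening will be recorded in the chart if performed, by clinical staff as per routine procedure". The treating team can therefore see the result. That sentence does not name SpCO, but section 1.1 says of emergency departments that "some (such as Rhode Island Hospital) also measure SpCO". Section 1.1 also reports that screening of this kind at that hospital found that "1-4/10,000 patients had unsuspected (both to the patient and clinician) COP".

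Recruitment has two strands. One is a convenience sample of patients having a CBC or an IV catheter. The other is targeted. Section 5.4 and section 7 (Stage 2) provide for approaching patients with known CO exposure, and Stage 2 states: "Research staff will be notified of any patient presenting to the emergency department with suspected CO exposure or toxicity". The triggers written down are exposure (fire rescue is the example) and signs and symptoms. A pulse CO-oximeter reading is neither listed nor ruled out.

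On the device, section 1.2 states: "The device is a more compact version of 510(k) cleared Rad-57 and Pronto devices". Section 1.1 says the new platform has modifications that may improve its performance.

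The quantity at issue is SpCO item 2 in section 2: sensitivity, specificity and false results against blood COHb, with a true positive set at COHb of 7 or above. No section asks for the reason for approach or the triage SpCO value as a study variable. No section plans accuracy results by stage or entry route.

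**The concern.** Sensitivity is the share of CO-positive patients whom the study device detects. If some of those patients are in the study because a related device had already read high, the case group is tilted towards patients this technology detects well. Two things cause the tilt. Errors of two similar devices on the same patient are likely to be correlated, so a patient the cleared device overreads is less likely to be missed by the study device. A high triage reading also favours patients with truly higher COHb, who are easier to detect with any device.

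The non-cases can be affected too. A false-high triage reading can bring in a patient with low COHb whom the study device may also overread, which lowers specificity.

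The study's stated purpose is the clinical utility of triage screening. A sensitivity estimated partly in patients already screened by SpCO may not carry over to patients who have not been. Without the entry route, nobody can tell afterwards whether this happened.

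**Working it through.** **The plan's own figures.** Section 5.1 gives about 1000 subjects at each of three sites, and 3 × 1000 = 3000 agrees with its total. It gives no target sensitivity, precision or number of CO-positive subjects, so there is no accuracy calculation to reproduce.

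**Where the CO cases will come from.** Expected occult cases among 3000 unselected patients = 3000 × rate.
- At 1 to 3 per 10,000 (section 5.1): 0.3 to 0.9.
- At 4 per 10,000 (upper figure in section 1.1): 1.2.

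The convenience sample will supply almost no occult poisonings, so poisoned subjects will come mostly from targeted recruitment. Some smokers in the convenience sample may also reach COHb 7; the documents give no rate. How targeted patients are found therefore matters for item 2.

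**Size of the bias.** Let s be the sensitivity in all cases, q the sensitivity in triage-flagged cases, and f the share of cases enrolled because of a triage reading, the rest being a representative draw. Then

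measured sensitivity = (1 − f)s + fq, and bias = f(q − s).

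The documents give none of s, q and f. The following are assumptions: COHb in cases is 7 plus an exponential with mean 6; both devices have normal error with SD 3 or 4 points; error correlation between devices is 0.3 to 0.7, with 0 added for comparison; the study SpCO is positive at 7 or above; the triage flag is at 10 or above. Results by simulation:

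| Error SD | Correlation | All cases (s) | Flagged (q) | Bias, f = 10% | Bias, f = 50% | Unflagged cases |
|---|---|---|---|---|---|---|
| 3 | 0 | 85.0% | 92.4% | +0.7 | +3.7 | 72% |
| 3 | 0.3 | 85.0% | 95.1% | +1.0 | +5.1 | 67% |
| 3 | 0.7 | 85.0% | 98.7% | +1.4 | +6.9 | 61% |
| 4 | 0 | 81.5% | 88.4% | +0.7 | +3.4 | 70% |
| 4 | 0.3 | 81.5% | 92.0% | +1.0 | +5.2 | 64% |
| 4 | 0.7 | 81.5% | 97.2% | +1.6 | +7.8 | 55% |

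Example (last row): q − s = 97.2 − 81.5 = 15.7 points; 10% of that is about 1.6 and 50% is about 7.8.

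- With f = 0 the bias is nil.
- With the flag at 7 or above and correlation 0.3 to 0.7, q is 88 to 94% and the bias at f = 50% is about +3 to +5 points.
- With uncorrelated errors, q still exceeds s by about 3 points (flag at 7) or 7 points (flag at 10). That part is selection of higher COHb, not shared device error.

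**A second model** drops the COHb distribution. It gives both devices the same sensitivity and a latent-normal correlation of 0.3 to 0.9 between their results. At f = 50%, a true 70% becomes 72.7 to 80.5%, and a true 90% becomes 90.6 to 93.3%. The direction is the same, and the bias shrinks as true sensitivity rises.

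**What exclusion would do.** The last column shows the extreme case. If every patient were triage-screened and every flagged case were dropped, the remaining cases would show 55 to 67% sensitivity (correlation 0.3 to 0.7) against a true 82 to 85%.

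**The case against.** The strongest reply is that the route is a reader's inference. The triage sentence in section 5.4 speaks of oximeters generally. Section 1.1 says only some departments measure SpCO, and the text available does not show how many of the three sites do. The written triggers are exposure and symptoms. This stands: the protocol leaves the route open but does not prescribe it.

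A reader might go further and infer that sensitivity will be overstated because the device's misses are removed before they can be counted. The documents do not support that. Triage-negative patients stay eligible through exposure history, a broad symptom list and the convenience sample, and enrolled patients are all planned to have blood COHb. The problem is possible over-representation of flagged cases, not loss of the others.

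It is also fair that nothing supports a share as high as 50%. The only documented yield of triage SpCO is 1 to 4 unsuspected cases per 10,000 patients, and a fire victim with a high reading would be approached anyway. Part of the bias is ordinary enrichment for higher COHb, which recruiting fire victims also produces. The platform's modifications leave the error correlation unknown.

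Finally, Stage 2 recruits are described as a separate arm, triage results are charted, and the CRF list in section 9.4 is open-ended. That helps only in part. Stage separates targeted from convenience recruits, but not those approached on a device reading from those approached on history or symptoms, and no analysis by either split is stated.

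**Conclusion.** The concern holds in conditional form. At any site that measures SpCO at triage, a high reading can lead to recruitment as a suspected CO case. Pooled SpCO sensitivity for COHb of 7 or above may then be overstated, and false-high flags may lower specificity. Both models put the sensitivity bias in one direction; its size cannot be assessed from what the protocol plans to collect and analyse. With a flag at 10 or above and error correlation 0.3 to 0.7, it runs from nil (no case enters this way), through about +1 to +1.6 points (10% of cases), to about +5 to +8 points (50% of cases). These figures rest on the assumed COHb distribution, error SDs, correlation, cut-offs and shares, none of which the documents give. The effect on specificity was not quantified.

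A reader might also infer that all device-prompted subjects should be removed from the main analysis. That does not follow: where patients are routinely triage-screened, it leaves too many triage-negative cases and can bias sensitivity downwards by more than the bias it is meant to cure.

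**What to change.** 1. Add to the CRF the reason for approach, in three categories: convenience sample; exposure history or symptoms; pulse CO-oximeter reading alone. Add any triage SpCO value already in the chart.
2. Prespecify SpCO sensitivity and specificity by entry route. Show the overall result with and without subjects approached solely because of a pulse CO-oximeter reading.
3. State in advance that the screening claim will be limited if results differ by route.
4. Do not make the set without those subjects the sole main analysis. Keep them in the agreement and elimination analyses.

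The cost is one CRF item, one added table and wider intervals within each route, because CO-positive subjects will be few. Clinical care and enrolment are unchanged.

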## 2 STUDY OBJECTIVES

The purpose of this study is to determine the clinical utility of triage screening for anemia and COP in the ED setting.

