## **9 DATA MANAGEMENT**

### **9.1 Provisions to Protect the Privacy Interests of Subjects**

Potential study candidates will be identified in real time, as they arrive and register in the emergency department. Research staff will check with the provider to ensure the subject's appropriateness. Subjects will only be approached about the study in private treatment rooms in the emergency department. The research staff will provide the consent form in person and give the prospective subject sufficient time to review the consent form and discuss the study with friends and family.

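### Stage 1 is a convenience sample with no approach order and no record of eligible patients passed over, so SpHb screening accuracy is open to selection bias of unknown size and direction

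*Combined protocol and SAP*

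**What the plan says.** Section 2 gives the purpose of the study: to "determine the clinical utility of triage screening for anemia and COP in the ED setting". For the general sample, section 5.4 (Subject Recruitment) specifies "A convenience sample of patients aged 1 year and up presenting to the emergency department for any complaint", restricted to patients whose own provider has decided on a CBC or an IV line. These patients "will be approached by trained research staff for evaluation for enrollment in the study". I read this group as Stage 1 of section 7. Section 9.1 adds a step before the approach: "Research staff will check with the provider to ensure the subject's appropriateness". It gives no criteria for that judgment.

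Section 5.4 and Stage 2 of section 7 also direct staff to seek out patients with known or suspected CO exposure or with anemia.

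The SpHb primary objectives in section 2 are accuracy for anemia against the hospital laboratory, and a threshold predicting acute treatment of anemia (transfusion, admission for anemia workup, or the operating room). The threshold is set on the first 500 subjects per institution, pooled, and validated on a second 500 per institution. The objectives do not say whether Stage 2 patients count toward these sets.

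The text gives no order of approach, no rule for which hours are covered, and no log of eligible patients who were not approached or who declined. Under section 9.4, case report forms are kept for enrolled subjects.

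**The concern.** Sensitivity and specificity depend on the mix of patients in whom they are measured. If the chance of being approached is related to anything that affects SpHb performance, such as severity of anemia, perfusion or stability, the estimates describe the enrolled mix and not the patients who arrive at triage.

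Staff have free choice of whom to approach, and other rules make unstable patients harder to enroll: approach only in private rooms, time to read the form and talk it over, full written consent, exclusion when surrogates disagree, and no delay to care (sections 5.4, 7 and 9.1). Each rule is reasonable. Yet section 1.1 justifies SpHb by hemorrhage and critical anemia, so these are patients the test is meant to find.

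The validation step offers no protection. Both sets of 500 pass through the same selection, so agreement between them would show stability within that route only. Without a record of who was passed over, the question could not be answered after the study either.

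**Working it through.** **1. The plan's own figures.** Section 5.1 gives three sites of about 1000: 3 × 1000 = 3000. Section 2 gives two sets of 500 per institution: 3 × (500 + 500) = 3000. Both reproduce the stated minimum of 3000. The two sets therefore use up the expected enrollment at each site. If Stage 2 patients count toward the 1000, they fall within the threshold and validation sets.

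**2. Can the bias be computed?** No. The documents give no expected sensitivity or specificity, no outcome frequency, no eligible volume and no approach rates. What follows is an illustration in which every input is assumed.

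**3. Formula.** Let half of the outcome-positive patients be unstable. Let r be their rate of approach relative to the others, and Se_u and Se_o the sensitivities in unstable and other patients:

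observed sensitivity = (0.5 r Se_u + 0.5 Se_o) / (0.5 r + 0.5)

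**4. SpHb assumed worse in unstable patients** (Se_u = 0.60, Se_o = 0.85):
- r = 1: (0.300 + 0.425) / 1 = 72.5%, the true value
- r = 0.5: (0.150 + 0.425) / 0.75 = 76.7%
- r = 0.25: (0.075 + 0.425) / 0.625 = 80.0%

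**5. SpHb assumed better in unstable patients** (Se_u = 0.95, Se_o = 0.80), for instance because their hemoglobin lies far below any threshold:
- r = 1: (0.475 + 0.400) / 1 = 87.5%, the true value
- r = 0.5: (0.2375 + 0.400) / 0.75 = 85.0%
- r = 0.25: (0.11875 + 0.400) / 0.625 = 83.0%

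The error is +4.2 or +7.5 points in step 4, and −2.5 or −4.5 points in step 5. With equal approach rates it is zero.

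**6. Smaller hard-to-measure groups.** Suppose a share h of positives is hard to measure, with sensitivity 0.60 to 0.80 against 0.90 in the rest, and h is 10% to 30%. At half the approach rate the overstatement is 0.5 to 3.7 points. At the upper end: (0.7 × 0.90 + 0.15 × 0.60) / 0.85 = 84.7%, against a true 0.7 × 0.90 + 0.3 × 0.60 = 81.0%. The effect thus runs from negligible to material.

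**7. Is there room for an arrival-order rule?** Section 5.4 gives 10 patients a day and a window from October 1, 2016 to December 31, 2018, which is 822 days. If 10 is the overall rate, 3000 / 10 = 300 days; the window needs only 3000 / 822 = 3.6 a day. If 10 is per site, 3000 / 30 = 100 days. Either way there is slack, although staffing hours and refusal rates are not given.

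**The case against.** The strongest reply is that the plan works against losing sick patients. Section 5.4 allows surrogate consent for serious or life-threatening conditions. The CBC or IV requirement favors sicker patients. Sections 5.4 and 7 have staff actively approach patients with anemia. Convenience sampling is openly declared, and the provider check sits under privacy protections, so calling it a severity filter is inference.

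Much of this stands, and it rules out several stronger readings:

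- A reader might infer that accuracy will be overstated. The documents do not show this: step 5 of the working reverses the sign with equally arbitrary values.
- A reader might infer that the anemia-treatment outcome will be under-represented. If Stage 2 patients enter the sets of 500, the sample could instead be enriched for it.
- A reader might divide 10 a day by three sites and conclude that staff pick a few from many. Section 5.4 does not say whether 10 is per site or overall, and eligible volume is not given.
- A reader might attribute the loss of all hard-to-measure patients to staff choice. Part of it is by criterion: "Patients with fingernail polish, discoloration or trauma to fingers" are excluded in 5.3, and 5.2 requires that "At least one digit has acceptable width as measured by study-provided digit gauge".

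The reply does not close the gap. Permission for surrogate consent does not mean that such patients are approached. The CBC or IV requirement decides who is eligible, not who is chosen. Stage 2 adds patients whose condition is known or suspected; it does not make Stage 1 representative, and mixing the two changes the case mix again.

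**Conclusion.** The concern holds as a weakness of design and reporting. An unordered, unrecorded selection step, including an undefined provider check, comes before a primary accuracy estimate meant for triage screening, and the validation set shares it. The resulting bias in SpHb accuracy is of unknown size and direction. The illustrations range from no bias to several points either way, and they rest wholly on assumed sensitivities, shares and approach rates.

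It would also go too far to say that arrival order avoids the problem. Provider refusals, declined consent, surrogate failures, off-shift arrivals, the CBC or IV requirement, the finger criteria and Stage 2 targeting all remain. The gain is that selection is reduced and what is left can be seen.

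**What to change.** In section 5.4, for Stage 1, replace the convenience sample by this rule: during each staffed shift, approach eligible patients in order of registration, and after each enrollment take the next eligible arrival. Section 9.1 already has candidates identified as they register, so the information is at hand.

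In addition:
- Record each provider refusal with its reason.
- Keep a de-identified count of eligible patients not approached or declining, using only items known at screening (age group, sex, triage level), and report it beside the enrolled sample.
- Report SpHb accuracy for Stage 1 separately from the targeted Stage 2 patients.

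The log should not extend to later events such as transfusion in people who declined or were never approached. That needs chart follow-up, which appears to go beyond the HIPAA waiver in section 5.4, written for identifying prospective subjects. The IRB should confirm that the screening count itself is covered.

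The cost is protocol wording, a short log kept by the same staff in the same hours, and slightly slower daily accrual because staff can no longer pick quick enrollments. The sample size stays at 3000.
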